4 STATISTICAL ANALYSES

4.1 GENERAL CONSIDERATIONS

In general, continuous data will be summarized using the number of observations available, mean, standard deviation (SD), median, [Q1, Q3] minimum, and maximum. Categorical and ordinal data will be summarized using the count and percentage of participants.

The baseline value is defined as the last available value before or equal to the first dose of double-blind investigational medicinal product (IMP). For participants randomized but not exposed, the baseline value is defined as the last available value before or equal to the date and time of randomization.

Baseline eGFR is defined for each participant as the average of eGFR values assessed prior or equal to first IMP, or randomization for participants randomized and not exposed.

Baseline of patient daily diaries scores is defined for each participant as the average of the assessments during the 7 days prior the 1st IMP or prior randomization for participants randomized and not exposed.

Baseline of urine osmolality is defined as the average of the 3 separate assessments within the 3 days prior or equal to the baseline visit (Visit 3).

Primary efficacy analyses will be conducted on Stage 1 ITT population and on combined Stage 1 and Stage 2 ITT populations (see Section 3), including all data available at the time of database lock from baseline to Month 24:

• Participants from Stage 2 with an eGFR between 30 and 44.9 mL/min/1.73 m² at screening will not be included in the primary efficacy analysis. A supplemental descriptive efficacy analysis on these participants will be performed separately (see Section 3 and Section 4.3.2.4).

Safety analyses will be conducted in the extended combined Stage 1 and Stage 2 population (see Section 3) including all data available from baseline to the end of the 24-month double-blind treatment period. Unless otherwise specified, analyses will be performed by intervention group (and overall for baseline and demographics characteristics).

Observation period

The observation period will be divided into 4 segments:

- The **pre-treatment period** is defined as the period up to first IMP administration.
- The **treatment-emergent** (TE) **period** is defined as the period from the first IMP administration up to the last IMP administration in EFC15392 study +30 days or up to the first visit in LTS15823 study, whichever comes earlier. The treatment-emergent period includes the following 2 periods:

- The **on-treatment period** is defined as the period from the first IMP administration to the last administration of the IMP +1 day.
- The **residual treatment** period is defined as the period from the end of the ontreatment period to the end of the treatment-emergent period.
- The **post-treatment period** is defined as the period from the end of the treatmentemergent period.

The on-study observation period is defined as the time from the first administration of the IMP until the end of the study (defined as the last scheduled visit for those who completed the study and the end-of-study date collected on electronic case report form (e-CRF) page "Completion of End of Study" for those who did not complete the study. If death is the end-of-study reason, date of death will be used).

4.2 PARTICIPANT DISPOSITIONS

The number (%) of participants included in each of the analysis populations listed in Table 4 will be summarized. The reasons for exclusion from the population without trial impact (disruption) due to COVID19 will be also summarized.

Screen failures are defined as participants who consent to participate in the study but are not subsequently randomized. The number (%) of screen failures and reasons for screen failures will be provided in the screened population.

The number (%) of participants in the following categories will be provided:

- Randomized participants.
- Randomized but not exposed participants.
- Randomized and exposed participants.
- Participants who completed the study treatment period as per protocol.
- Participants who did not complete the study treatment period as per protocol and main reason for permanent intervention discontinuation.
- Participants who completed the study period as per protocol.
- Participants who did not complete the study period as per protocol and main reason for study discontinuation.

Reasons for permanent study intervention and study discontinuation "adverse event" and "other reasons" will be split as related versus not related to Covid-19, if applicable.

The number (%) of exposed and not randomized participants will also be summarized.

In addition, the number (%) of participants screened, screened-failed, randomized, with permanent intervention discontinuation and with early study discontinuation will be provided by country and site.

Protocol deviations

Critical and major protocol deviations (automatic or manual) will be summarized in the randomized population as well as displayed separately as related versus not related to Covid-19.

Disposition by visit

Participant disposition by visit will be provided according to trial impact (disruption) due to COVID19, as reported in CRF.

4.3 PRIMARY ENDPOINT(S) ANALYSIS

4.3.1 Stage 1

4.3.1.1 Definition of endpoint(s)

In Stage 1, the primary efficacy endpoint is the annualized rate of change in TKV based on MRI from baseline to 18 months. All the efficacy assessments collected during the study will be used, including those obtained after IMP discontinuation.

The primary estimand will be the difference in mean slope of log10-transformed TKV estimated from baseline to 18 months in all randomized participants, regardless of whether or not participants completed the treatment period. This estimand corresponds to a "treatment policy strategy". This estimand will be considered primary for supporting regulatory decision making.

A second estimand will be the difference in the mean slope of log10-transformed TKV estimated during the on-treatment period (from baseline to end of treatment). This estimand corresponds to "while on-treatment strategy" and will be evaluated for the primary efficacy endpoint only. This estimand will be considered for describing the effect of treatment as long as participants adhere to their randomized treatment.

4.3.1.2 Main analytical approach

A linear mixed effect model will be fitted to the log10-transformed TKV, which will include fix effects of treatment (venglustat 15 mg, venglustat 8 mg or placebo), Mayo Imaging Classification (as per randomization stratification factor: class 1C versus 1D versus 1E), time (as continuous variable), treatment * time interaction and Mayo Imaging Classification * time interaction, and will include random intercept and slope. Time will be based on actual TKV assessment date relative to randomization date (in years).

Within group mean slope of log10-transformed TKV will be obtained from the linear mixed effect model, using weights for each stratum (Mayo class 1C, 1D and 1E) equal to the overall proportion of participants in each stratum in the Stage 1 ITT population (ie, "population weight"). A backtransformation will be applied to obtain annualized rate of change in TKV (in % per year) within each treatment arm, along with their 95% confidence intervals (CI).

Overall effect of venglustat will be assessed using a Multiple Comparison Procedure. Multiple trend tests will be performed using optimal contrasts determined from a set of 3 prespecified candidate models for the dose-response relationship described in Figure 1.

[figure not shown]

Figure 1 - Prespecified candidate of dose-response models

Optimal contrasts for each candidate model were derived using the R add-on package DoseFinding (2, 3) and are presented in Table 5. Contrasts will apply to treatment * time interaction term in the linear mixed effect model. P-value from the Multiple Comparison Procedure will be calculated as described in Section 5.6.3.

Linear model Dose E_{max} model Sigmoid E_{max} model Placebo -0.8131 -0.7223-0.6615GZ/SAR402671 8 mg 0.3424 0.0314 -0.0838 GZ/SAR402671 15 mg 0.4707 0.6909 0.7453

Table 5 - Optimal contrasts for the 3 prespecified candidate of dose-response models

Relative reduction in annualized rate of change in TKV will be estimated for each dose of venglustat versus placebo and defined as:

Relative reduction (%) =
$$\left(1 - \frac{\text{Annualized rate of change in TKV in GZ/SAR4026 71 arm}}{\text{Annualized rate of change in TKV in placebo arm}}\right) \times 100$$

Relative reduction for each dose of venglustat will be presented with 95% confidence intervals obtained using Fieller method (see Section 5.6.2) only if significant change is observed in the

placebo arm at the 0.05 level. In addition, p-values for the comparison of each dose of venglustat versus placebo will be presented for descriptive purpose.

Handling of missing data

The primary analysis will include all observed TKV data in randomized participants, regardless of whether or not participants completed the treatment period (treatment policy strategy). participants who prematurely and permanently discontinue study intervention will be requested to obtain an MRI scan at 18 months and their data collected after permanent intervention discontinuation will be included in the primary analysis.

No imputation of missing data will be performed. The linear mixed effect model described above will be run on all observed data, including data collected after intervention discontinuation.

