## 6 STUDY DESIGN

### 6.1 DESCRIPTION OF THE STUDY

This is an international, multicenter, randomized, double-blind, placebo-controlled, two-stage study in adult patients at risk of rapidly progressive ADPKD aged 18 to 50 years in Stages 1 and 2 (and aged 18 to 55 years for patients with a screening eGFR between 30 and 44.9 mL/min/1.73 m^2 in Stage 2).

The study is divided into 2 stages:

**Stage 1:** An up to 30-day screening period including a 2-week single-blind placebo run-in (to identify patients who are unlikely to follow the assigned treatment regimen), followed by a randomized double-blind comparative placebo-controlled core treatment period of 24 months duration.

After run-in, eligible patients will be randomized with a 1:1:1 ratio to placebo, 8 mg venglustat, or 15 mg venglustat.

Patients will be stratified based on their predicted ADPKD progression rate (1C versus 1D versus 1E) according to Mayo Imaging Classification and by geographic region (North America, Europe, China, Japan, Republic of Korea, Rest of the World). If after reviewing the unblinded aggregate safety data from Stage 1 (after at least 1 month of treatment of the first 150 randomized patients from Stage 1), the DMC recommends the 8 mg dose for Stage 2, then the DMC may recommend switching patients on 15 mg treatment arm, in Stage 1, to the 8 mg arm.

**Stage 2:** After the first 150 randomized patients from Stage 1 have completed at least 1 month of treatment (or have prematurely discontinued), the DMC will review in an unblinded fashion the aggregate safety data from Stage 1 and will select the venglustat dose 8 mg or 15 mg for Stage 2 patients. The selected dose will be the highest dose determined to be safe and well tolerated in Stage 1. If after reviewing the unblinded aggregate safety data from Stage 1, the DMC recommends the 8 mg dose for Stage 2, then the DMC may recommend switching patients on the 15 mg treatment arm, in Stage 1, to the 8 mg arm.

Stage 2 will start with an up to 30-day screening period including a 2-week single-blind placebo run-in (to identify participants who are unlikely to follow the assigned treatment regimen), followed by a randomized double-blind comparative core treatment period of 24 months duration.

After run-in, patients will be randomized with a 1:1 ratio to placebo and venglustat (dose to be determined in Stage 1).

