### 9.4.2 Estimated glomerular filtration rate

Estimated glomerular filtration rate will be calculated from the creatinine result from the general chemistry laboratory assessments according to the study flow charts ([Section 1.3](#) and [Section 1.4](#)). The CKD-EPI equation will be used:

$$\text{eGFR} = 141 \times \min(\text{SCr}/\kappa, 1)^\alpha \times \max(\text{SCr}/\kappa, 1)^{-1.209} \times 0.993^{\text{Age}} \times 1.018 \text{ (if female)} \times 1.159 \text{ (if Black)}$$

Where:

- SCr is serum creatinine in mg/dL.
- $\kappa$  is 0.7 for females and 0.9 for males.
- $\alpha$  is -0.329 for females and -0.411 for males.
- Min indicates the minimum of SCr/ $\kappa$  or 1, and
- Max indicates the maximum of SCr/ $\kappa$  or 1.
- For calculation of eGFR in Asian population of patients (except Japanese patients), the Asian-modified CKD-EPI (aCKD-EPI) equation will be used ([14](#)):

$$\text{Female and SCr} \leq 0.7: 151 \times (\text{SCr} / 0.7)^{-0.328} \times (0.993)^{\text{age}}$$

$$\text{Female and SCr} > 0.7: 151 \times (\text{SCr} / 0.7)^{-1.210} \times (0.993)^{\text{age}}$$

$$\text{Male and SCr} \leq 0.9: 149 \times (\text{SCr} / 0.9)^{-0.412} \times (0.993)^{\text{age}}$$

$$\text{Male and SCr} > 0.9: 149 \times (\text{SCr} / 0.9)^{-1.210} \times (0.993)^{\text{age}}$$

- For calculation of eGFR in Japanese patients, CKD-EPI Study equation multiplied by a Japanese coefficient of 0.813 will be used ([15](#)).

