##### **11.4.2.2.2 Stage 1: Change in pain (BPI- Item 3) from baseline to 18 months**

In Stage 1, change in pain from baseline to 18 months is a secondary efficacy endpoint. Pain score will be based on BPI Item 3, assessed from the daily symptom diary.

Daily diaries scores will be averaged over 7 consecutive assessments prior to the baseline, Month 3 and Month 12 visit and over the 14 consecutive days prior to the planned Month 18 visit. At least 50% of the days in the observation period (ie, 4 or more of the 7 days for baseline, Month 3 and Month 12; 7 or more of the 14 days for Month 18) are required to calculate the average score on-missing data.

Change in pain from baseline will be analyzed using a mixed effect model with repeated measures (MMRM). The model will include the fixed categorical effects of treatment (venglustat 15 mg,

venglustat 8 mg, or placebo), Mayo Imaging Classification (as per randomization stratification factor: Class 1C versus 1D versus 1E), time point (Month 3, Month 12, Month 18), treatment-by-time point interaction, randomization strata-by-time point interaction as well as the continuous fixed covariates of baseline and the baseline-by-time point interaction.

This model will be run using SAS Mixed procedure with an unstructured correlation matrix to model the within-patient errors. Parameters will be estimated using restricted maximum likelihood method. Denominator degrees of freedom will be estimated using Kenward-Roger approximation. This model will provide baseline adjusted least-squares means estimates at Month 18 for each treatment groups with their corresponding standard errors (SE) and 95% confidence intervals (CI). Within group mean change in pain will be obtained from the MMRM, using weights for each stratum (Mayo Class 1C, 1D and 1E) equal to the overall proportion of patients in each stratum in the Stage 1 ITT population (ie, “population weight”).

Overall effect of venglustat will be assessed using a Multiple Comparison Procedure similar to those of the primary endpoint (see [Section 11.4.2.1](#)). In addition, p values for the comparison of each dose of venglustat versus placebo will be presented for descriptive purpose.

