1 INTRODUCTION

1.1 STUDY DESIGN

This is an international, multicenter, randomized, double-blind, placebo-controlled, two-stage study in adult participants at risk of rapidly progressive Autosomal Dominant Polycystic Kidney Disease (ADPKD) aged 18 to 50 years in Stages 1 and 2. In addition, Stage 2 also includes participants aged 18 to 55 years with a screening estimated Glomerular Filtration Rate (eGFR) between 30 and 44.9 mL/min/1.73 m².

The study is divided into 2 stages:

Stage 1: an up to 30-days screening period including a 2-week placebo run-in (to identify participants who are unlikely to follow the assigned treatment regimen), followed by a randomized, double-blind, comparative placebo-controlled core treatment period of 24 months duration.

After run-in, eligible participants, aged 18 to 50 years with an eGFR in (45 to 89.9) are randomized with a 1:1:1 ratio to placebo, 8 mg venglustat, or 15 mg venglustat.

Participants are stratified based on their predicted ADPKD progression rate (1C versus 1D versus 1E) according to Mayo Imaging Classification and geographical region (North America, Europe, China, Republic of Korea, Rest of the World).

After the interim unblinded aggregate safety review by the DMC of the first 150 randomized participants from Stage 1 having completed at least 1 month of treatment (or have prematurely discontinued), the DMC determined that the 15 mg dose was the highest dose to be safe and well tolerated in Stage 1, and recommended the venglustat 15 mg dose for Stage 2.

Stage 2: starts with an up to 30-day screening period including a 2-week placebo run-in (to identify participants who are unlikely to follow the assigned treatment regimen), followed by a randomized, double-blind, comparative core treatment period of 24 months duration. After run-in, eligible participants aged 18 to 55 years with an eGFR of 30 to 89.9 are randomized with a 1:1 ratio to placebo and 15 mg venglustat. Participants are stratified based on their predicted progression rate (1C versus 1D versus 1E) according to Mayo Imaging Classification and geographical region (North America, Europe, China, Republic of Korea, Rest of the World).

Participants who completed 24 months of treatment in EFC15392 study may be given the option to enroll into an open-label long-term extension study LTS15823 (additional 24 months of treatment with 15 mg venglustat).

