4.3.2.2 Main analytical approach

The analysis of eGFR will be similar to those of TKV, with the exception that no log transformation will be used for eGFR (see Section 4.3.1.2).

Primary analysis in Stage 2 will combine all data from Stage 1 and Stage 2 available from baseline to the end of the 24-month double-blind core treatment period. Primary analysis will include all observed eGFR data in randomized participants, regardless of whether or not participants completed the treatment period (treatment policy strategy). Participants who prematurely and permanently discontinue study medication will be requested to obtain eGFR at 24 months.

No imputation of missing data will be performed.

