4.4.1.2 Main analytical approach

The analysis of eGFR in Stage 1 will be identical to those of Stage 2 (see Section 4.3.2.2).

Daily diaries scores will be averaged over 7 consecutive assessments prior to the baseline, Month 3 and Month 12 visit and over the 14 consecutive days prior to the planned Month 18 visit. At least 50% of the days in the observation period (ie, 4 or more of the 7 days for baseline, Month 3 and Month 12; 7 or more of the 14 days for Month 18) are required to calculate the average score on non-missing data (4, 5).

Change in pain and change in fatigue from baseline to 18 months will be analyzed on the ITT population, regardless of whether or not participants completed the treatment period, using a mixed effect model with repeated measures (MMRM). The model will include the fixed categorical effects of treatment (venglustat 15 mg, venglustat 8 mg or placebo), Mayo Imaging Classification (as per randomization stratification factor: Class 1C versus 1D versus 1E), time point (Month 3, Month 12, Month 18), treatment-by-time point interaction, randomization strataby-time point interaction as well as the continuous fixed covariates of baseline and the baseline-by-time point interaction.

This model will be run using SAS Mixed procedure with an unstructured correlation matrix to model the within-patient errors. Parameters will be estimated using restricted maximum likelihood method. Denominator degrees of freedom will be estimated using Kenward-Roger approximation. This model will provide baseline adjusted least-squares means estimates at Month 18 for each study intervention groups with their corresponding standard errors (SEs) and 95% confidence intervals (CI). Within group mean change in pain will be obtained from the MMRM, using weights for each stratum (Mayo Class 1C, 1D and 1E) equal to the overall proportion of participants in each stratum in the Stage 1 ITT population (ie, "population weight"). Population weights are considered more appropriate than equal coefficients due to expected unbalances in the study population between levels of the randomization stratification factors.

Overall effect of venglustat will be assessed using a Multiple Comparison Procedure similar to those of the primary endpoint (see Section 4.3.1.2). In addition, p values for the comparison of each dose of venglustat versus placebo will be presented for descriptive purpose.

There will be no imputation of missing data.

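### Region is a randomisation stratum but is missing from the main TKV and eGFR slope models and from the main effects of the pain/fatigue MMRM, with no reason given: a small, conservative loss of precision

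*SAP*

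**What the plan says.** **Randomisation.** Protocol 6.1 stratifies both stages by Mayo class and "by geographic region (North America, Europe, China, Japan, Republic of Korea, Rest of the World". SAP 1.1 gives a different list for the same factor: "geographical region (North America, Europe, China, Republic of Korea, Rest of the World", without Japan. SAP 4.3.1.5 and SAP Appendix 3 list six regions, as the protocol does.

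**TKV slope model (SAP 4.3.1.2).** The stratification term is "Mayo Imaging Classification (as per randomization stratification factor: class 1C versus 1D versus 1E), time (as continuous variable". The remaining terms are treatment, "treatment * time interaction and Mayo Imaging Classification * time interaction, and will include random intercept and slope". Region is not among them.

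**eGFR slope model (SAP 4.3.2.2).** "The analysis of eGFR will be similar to those of TKV, with the exception that no log transformation will be used for eGFR". Region is therefore absent here too.

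**Pain and fatigue MMRM (SAP 4.4.1.2, Protocol 11.4.2.2.2).** The categorical effects include "Mayo Imaging Classification (as per randomization stratification factor: Class 1C versus 1D versus 1E), time point (Month 3, Month 12, Month 18". The model also has an interaction of the randomisation strata with time point, "as well as the continuous fixed covariates of baseline and the baseline-by-time point interaction". Region is not named as a main effect.

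**Where region does appear.** SAP 4.3.1.5, carried over to eGFR by 4.3.2.5, adds region-by-time, treatment-by-region and treatment-by-region-by-time terms to the primary model for the region subgroup analysis.

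**History.** The Amendment 02 entry in Protocol Appendix N says region was added as a stratum to balance the arms across regions. It also records that the analysis adjusts for Mayo class, without saying why region is left out.

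**The concern.** Stratifying on a factor removes its between-stratum part from the true sampling variance of the treatment difference. If the model omits that factor, the same part stays in the estimated between-patient slope variance. To the extent that the factor predicts slope, the model-based standard error then exceeds the true one. Type I error is protected, but confidence intervals are wider than they need to be and some power is lost. Here the loss would fall on both primary endpoints, although region is already recorded at randomisation and coded for the subgroup analyses.

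The text is also unclear in two places. SAP Appendix 3 defines the randomisation strata as Mayo class and region together, so the MMRM's strata-by-time-point interaction can be programmed with or without region. The five-region list in SAP 1.1 conflicts with the six-region list elsewhere.

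**Working it through.** **1. The plan's own power.** The design in SAP 5.5 was re-simulated with 10,000 trials per scenario, treating the variance components as known instead of estimating them by REML. Scenario 2 gave 89.2% for TKV (stated 89.0%) and 87.1% for eGFR overall (stated 87.0%). The analysis models coded in SAP 5.5 contain dose, time and their interaction, with neither Mayo class nor region. The stated power therefore does not depend on whether region is adjusted for.

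**2. A yardstick for region.** The documents give no slopes by region, so the plan's other stratifier, Mayo class, is used for scale. Slopes and the 50/33/17% mix are from Protocol 11.1.
- eGFR: the mean is -3.66. The between-class variance is 0.50 × 0.498² + 0.33 × 0.222² + 0.17 × 1.032² = 0.321, so the SD is 0.57 mL/min/1.73 m²/year. Against a slope variance of 1.98² = 3.92, that is 8.2%.
- TKV: the mean is 0.02764. The same calculation gives 4.07 × 10⁻⁶, so the SD is 0.0020 log10/year. Against 0.01477² = 0.000218, that is 1.9%.

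**3. Per-patient variance of a fitted slope.** With complete visits, v = residual variance / Sxx + slope variance, where Sxx is the sum of squared deviations of the visit times (years) from their mean. Variances are from Protocol Appendix J and visit times from SAP 5.5.
- eGFR to 24 months: Sxx = 4.506; v = 40.26/4.506 + 3.90 = 12.83.
- eGFR to 12 months: Sxx = 0.770; v = 40.26/0.770 + 3.90 = 56.2.
- TKV to 18 months: Sxx = 1.458; v = 0.000658/1.458 + 0.000218 = 0.000669.
- TKV to 9 months: Sxx = 0.338; v = 0.000658/0.338 + 0.000218 = 0.00216.

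**4. Overstatement of the SE.** If region has between-stratum slope variance τ², the ratio is √((v + τ²)/v). With τ² set to the Mayo-class value:

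| Data | Calculation | SE too large by |
|---|---|---|
| eGFR, 24 months | √(1 + 0.321/12.83) - 1 | 1.2% |
| eGFR, 12 months | √(1 + 0.321/56.2) - 1 | 0.3% |
| TKV, 18 months | √(1 + 4.07×10⁻⁶/0.000669) - 1 | 0.3% |
| TKV, 9 months | √(1 + 4.07×10⁻⁶/0.00216) - 1 | 0.1% |

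**5. Larger assumed effects.** Region SDs of 0.5 to 1.0 for eGFR give 1.0% to 3.8% at 24 months and 0.2% to 0.9% at 12 months. SDs of 0.003 to 0.006 for TKV give 0.7% to 2.7% at 18 months. Apart from the 0.5 for eGFR, these SDs exceed the Mayo yardstick; 1.0² is about 26% of the 3.90 slope variance.

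**6. Effect on power.** In the same simulation, removing 10% of the slope variance moved power from 89.2% to 89.7% (TKV) and from 87.1% to 87.9% (eGFR). Removing 20% moved it to 91.2% and 89.7%. The Monte Carlo SE is about 0.3 points.

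**The case against.** **The gain is tiny and the timing is bad.** Adjustment for Mayo class alone dates from Amendment 02 (May 2018), before the first randomisation in February 2019. SAP version 2 is dated 22 June 2021, after the futility review of 14 May 2021, and SAP 4.9.2 provides for release of unblinded results to a small senior sponsor team once stopping is recommended. Changing the primary model then gives up pre-specification for about 1% of a standard error. Follow-up is also truncated: about 30% of Stage 1 had completed 18 months at the interim, and Stage 2 has no post-baseline MRI, so the shorter-follow-up rows of the table are the more relevant ones. This stands as an argument about how to act. It does not supply the missing reason for leaving region out, and a supplementary analysis meets it.

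**Three stronger readings are tempting, and the documents do not support them.**
- A reader might infer that every efficacy model ignores region. The subgroup models in SAP 4.3.1.5 and 4.3.2.5 include it, and the MMRM's strata-by-time-point term may do so.
- A reader might infer that eGFR slopes differ by region by construction, because for Japanese patients the "CKD-EPI Study equation multiplied by a Japanese coefficient of 0.813 will be used". Protocol 9.4.2 selects the equation by patient population, not by region stratum. The multiplier is constant within a patient. It turns -3.66 into 0.813 × -3.66 = -2.98, but the random intercept and slope absorb this. The equation for other Asian patients scales by about 1.05 to 1.06 above the creatinine knot (151/(141 × 1.018) and 149/141). Assuming 5% to 20% Japanese and 5% to 20% other Asian patients, the equations together raise the eGFR SE by only about 0.1% to 0.4%.
- A reader might infer that the error bars are wrong as a matter of fact. They are too wide only if region predicts slope, and the documents give no data on that.

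**Conclusion.** The point holds as a minor matter of efficiency and consistency. A stratification factor is left out of the main TKV and eGFR models and of the MMRM main effects without explanation. If region were as prognostic as Mayo class, the standard errors would be too large by about 1.2% (eGFR, 24 months) and 0.3% (TKV, 18 months), falling to about 0.3% and 0.1% with 12 and 9 months of data. If slopes do not differ by region, nothing is lost. The direction is conservative, the treatment estimates are not biased, and the stated 89% and 87% power is untouched.

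The size rests on three assumptions: Mayo class as the yardstick for an unknown region effect, complete visits, and the historical variance components in the protocol. The conflicting region lists and the unclear MMRM term rest on no assumption.

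**What to change.** 1. Add region as randomised and region-by-time to the TKV and eGFR slope models, and region and region-by-time-point to the MMRM. Extend to these models the SAP 4.3.1.5 rule that allows categories with fewer than 5 participants to be combined, and state the region weights used for the within-arm mean slopes, as is already done for Mayo class.
2. If the primary model must stay as pre-specified after the futility unblinding, run item 1 as a supplementary analysis under SAP 4.3.1.4, 4.3.2.4 and 4.4, and give one sentence on why region is not in the primary model. SAP 4.3.1.3 and 4.3.2.3 cancel all sensitivity analyses, so no overall region-adjusted treatment effect is currently planned.
3. State in SAP 4.4.1.2 whether the strata-by-time-point interaction includes region.
4. Reconcile the region list in SAP 1.1 with the protocol, SAP 4.3.1.5 and SAP Appendix 3.

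The cost is SAP wording and, with six regions, 5 + 5 = 10 extra fixed effects in each slope model, which is negligible against 240 to 560 planned patients. The MMRM needs 5 + 5 × 2 = 15 with three time points or 5 + 5 × 3 = 20 with four. Because the SAP already foresees that the MMRM may not converge, failure of the region-adjusted version should lead back to the Mayo-only model and not directly to descriptive summaries.
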